## 7.5.3. Recording of data

The use of black ink is required for subject completed questionnaires. If any changes are necessary, subjects must be instructed to make any changes by drawing a line through the undesired response, initialling the change, and then recording the desired response. Once a subject returns the questionnaire, no change will be allowed.

### 7.5.3.1. Collection and storage of subject questionnaires

Upon completion of the questionnaires, the investigator will retrieve the questionnaires from the subject, and check that the header section (Subject Number, Visit Date, etc) is completed. The investigator (or qualified designated member of their staff) will use the subject completed questionnaires to enter the recorded data into the appropriate section of the eCRF. The original version of the completed questionnaires will stay with the subject's source documents. A completed questionnaire should not be given back to the subject once it has been returned to the source documents

#### 7.5.4. Medical resource utilisation

At Visit 2 (Baseline) and each scheduled 13 week clinic visit post-randomisation, the investigator will record details of any health care utilisation associated with an episode of acute urinary retention, BPH-related prostatic surgery and/or other minimally-invasive prostatic procedures for treatment of BPH. The following information will be collected in the eCRF as follows:

• Incidence of hospital admissions for AUR and/or surgical interventions; number and type of procedures carried out

• Length of hospital stay (in days, hours) associated with incidence of AUR and/or surgical interventions, and associated ward type

## 7.6. Pharmacogenetics

An important objective of the clinical study is PGx research. Participation in PGx is optional but all subjects who are eligible for the clinical study will be given the opportunity to participate. Subjects may decline participation without effect on their medical care or care during the clinical study. A separate consent signature is required for PGx research.

Patients who provide consent will have a blood sample taken for analysis at Visit 2. The presence/absence of genetic variations in patient genes in DNA from blood will be analysed to determine their relationship with response (safety, tolerability, and efficacy) to treatment with either the combination of dutasteride and tamsulosin or tamsulosin alone.

Information regarding pharmacogenetic research is included in Appendix 1. The IEC/IRB and, where required, the applicable regulatory agency must approve the PGx assessments before these can be conducted at the site. The approval(s) must be in writing and will clearly specify approval of the PGx assessments (i.e., approval of Appendix 1). In some cases, approval of the PGx assessments can occur after approval is obtained for the rest of the study. If so, then the written approval will clearly indicate approval of the PGx assessments is being deferred and the study, except for PGx assessments, can be initiated. When PGx assessments will not be approved, then the approval for the rest of the study will clearly indicate this and therefore, PGx assessments will not be conducted.

## 7.7. Population Pharmacokinetics (Chinese Subjects Only)

A population pharmacokinetics (PPK) substudy will be performed only in subjects of Chinese origin, living in China, and participation in this substudy will be mandatory for these subjects. This substudy will estimate the PK parameters of dutasteride when dosed orally in combination (dutasteride 0.5 mg once daily and tamsulosin 0.2 mg once daily) in Chinese men with BPH. See Appendix 7 for more details on the PPK substudy.

Serum PK samples will be collected as indicated in Table 1. The actual date and time of each blood sample collection will be recorded, as well as the timing of the last dose of combination taken before the PK sample. Details of blood sample collection (including volume to be collected), processing, storage, and shipping procedures are provided in the SPM.

#### 8. DATA MANAGEMENT

For this study, data will be collected using defined electronic case report forms (eCRFs), transmitted electronically to GSK and combined with data provided from other sources in a validated data system.

Management of clinical data will be performed in accordance with applicable GSK standards and data cleaning procedures to ensure the integrity of the data, e.g., removing

errors and inconsistencies in the data. Adverse events and concomitant medications terms will be coded using MedDRA and an internal validated medication dictionary, GSK Drug. Laboratory data (i.e., hematology and clinical chemistry) will be stored in a database maintained by the central laboratory and transferred to GSK at agreed times.

An appropriate medical dictionary that covers all approved drugs in the region must be referenced.

eCRFs (including queries and audit trails) will be retained by GSK, and copies will be sent to the investigator to maintain as the investigator copy.

In all cases, subject initials will not be collected or transmitted to GSK according to GSK policy.

## 9. DATA ANALYSIS AND STATISTICAL CONSIDERATIONS

## 9.1. Hypotheses

The primary endpoint is change from baseline IPSS. Let the following represent the mean change from baseline IPSS for each treatment group:

Hdut+tam: combination (0.5mg dutasteride and 0.2mg tamsulosin) treatment group

Htam: 0.2mg tamsulosin treatment group

Then the primary null and alternative hypotheses to be tested at Year 2 are as follows:

Description	Null Hypothesis	Alternative Hypothesis
Combination versus 0.2mg tamsulosin	H dut+tam = H tam	H dut+tam ≠ H tam

Two-sided tests of the null hypothesis will be conducted at the 0.05 level of significance to show superiority of the combination treatment group compared to 0.2mg tamsulosin at 2 years of treatment.

## 9.2. Study Design Considerations

## 9.2.1. Sample Size Assumptions

The sample size was calculated based on estimates of IPSS change from baseline using information obtained from the CombAT study. Sample size estimates were computed in terms of a continuous response variable assuming a normal distribution, IPSS change from baseline mean difference between treatment groups of 1.8, a standard deviation of 6, and considering 90% power. With these assumptions, the required minimum sample size is 234 subjects per arm. Therefore, since a 20% treatment phase discontinuation rate is assumed, then randomization of 293 subjects per treatment arm (586 total) is required for 90% power.

## 9.2.2. Sample Size Sensitivity

Following is a chart showing scenarios of treatment differences of IPSS change from baseline after 2 years using assumptions above and the corresponding power estimates.

Scenario	IPSS change from baseline: difference in Combination and 0.2mg Tamsulosin	Power
Alternative #1	1.6	82%
Planned	1.8	90%
Alternative #2	2.0	95%

## 9.2.3. Sample Size Re-estimation

Sample size-re-estimation is not planned.

## 9.3. Data Analysis Considerations

## 9.3.1. Analysis Populations

The Intent-to-Treat (ITT) population will comprise all randomized subjects regardless of whether or not treatment was administered. This population will be based on the treatment to which the subject was randomized and will be the primary population for the analysis of efficacy and safety data. Any subject who receives a treatment randomisation number will be considered to have been randomized.

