## 2.2.2. Safety

The safety objective is to assess the safety and tolerability of co-administered dutasteride 0.5 mg once daily and tamsulosin 0.2 mg once daily compared to tamsulosin monotherapy 0.2 mg once daily.

The safety endpoints are presented in Section 7.3.1 of this protocol.

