#### **Secondary Analyses**

The year 2 secondary efficacy endpoints include: Qmax; prostate volume; IPSS improvement of  $\geq 2$  points,  $\geq 3$  points and, separately,  $\geq 25\%$  improvement from baseline; and Qmax improvement of  $\geq 3$ ml/sec and, separately,  $\geq 30\%$  improvement from baseline. Time to AUR or BPH-related surgical intervention is also a secondary efficacy endpoint.

The following describes the year 2 secondary efficacy endpoints and associated analyses. All treatment comparisons referenced are in terms of the combination therapy versus 0.2 mg tamsulosin.

 Prostate volume, change from baseline prostate volume, and percentage change from baseline prostate volume will be summarized by treatment group using both the LOCF and At Visit approaches at each scheduled post-baseline assessment.
 Percentage change from baseline prostate volume will be compared at each scheduled post-baseline assessment using the following general linear model:

log(post-baseline prostate volume/baseline prostate volume) = log(baseline prostate volume) + treatment + cluster

- Symptom improvement is measured using the IPSS and also evaluated using a categorical change from baseline improvement of ≥2 points and ≥3 points and, separately, ≥25% improvement from baseline. Treatment comparisons will utilise a Mantel-Haenszel test controlling for cluster at alpha=0.05.
- Maximum urinary flow (Qmax), change from baseline Qmax, and percentage change from baseline Qmax will be summarized by treatment group using both the LOCF and At Visit approaches at each scheduled post-baseline assessment. Change from baseline Qmax will be compared at each scheduled post-baseline assessment using a general linear model with effects for treatment, cluster, and baseline Qmax.
- Qmax improvement of ≥3mL/sec and, separately, ≥30% improvement from baseline will be computed by treatment group. Treatment comparisons will utilise a Mantel-Haenszel test controlling for cluster at alpha=0.05.
- Time to first AUR or BPH-related surgical intervention will be defined as the number of days from date of first dose of randomized study drug to date of the first event (earliest occurring of either AUR or BPH-related surgery) for each subject. Censoring will occur at the earliest of the following dates as applicable: the date of prostatectomy, the date of last contact for AUR and surgical intervention assessment,

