#### 9.3.7.2. Safety Analyses

The Intent-to-Treat population will be used for the analysis of safety data. Complete details of the safety analyses will be provided in the RAP.

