#### **Adverse Events**

Adverse events (AEs) will be coded using Medical Dictionary for Regulatory Activities (MedDRA). The frequency of events, the frequency of subjects and the percentage of subjects reporting each adverse event will be summarized by treatment group for all AEs and separately for drug-related AEs. The proportion of subjects reporting at least one AE, at least one drug-related AE, at least one serious AE, and at least one AE leading to withdrawal will be computed for each treatment group. Comparisons of treatment groups for each of these sets of AEs will be performed using Fisher's exact test.

Special interest adverse events will be defined in the RAP.

The incidence of deaths and the primary cause of death will be summarized.

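### The main safety analysis is fixed in all randomised men by assigned arm, dosed or not; the numerical effect is probably very small, but a dosed, as-received safety population costs almost nothing

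*Protocol*

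**What the plan says.** Section 9.3.1 states that the ITT population "will comprise all randomized subjects regardless of whether or not treatment was administered". It adds that "Any subject who receives a treatment randomisation number will be considered to have been randomized", and that the population is "based on the treatment to which the subject was randomized and will be the primary population for the analysis of efficacy and safety data". Section 9.3.7.2 says the same again: "The Intent-to-Treat population will be used for the analysis of safety data". The only other populations defined are Per Protocol (9.3.2) and PPK (9.3.3). There is no safety or as-treated set and no rule for analysing safety by treatment received.

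The safety objective in Section 2.2.2 is "to assess the safety and tolerability of co-administered dutasteride 0.5 mg once daily and tamsulosin 0.2 mg once daily compared to tamsulosin monotherapy". Under Adverse Events in Section 9.3.7.2, "the percentage of subjects reporting each adverse event will be summarized by treatment group for all AEs and separately for drug-related AEs", and "Comparisons of treatment groups for each of these sets of AEs will be performed using Fisher's exact test". Section 9.3.7.2.1 also uses Fisher's exact test for breast examination findings and for abnormal changes in blood pressure, pulse and DRE.

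For the secondary endpoint of AUR or BPH-related surgery, Section 9.3.7.1 defines time to event as the "number of days from date of first dose of randomized study drug" to the first event, and then specifies the log-rank comparison in the ITT population.

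**The concern.** The safety objective asks what happens to men who take the combination compared with men who take tamsulosin alone. Grouping all randomised men by assigned arm is the right default for efficacy, where it protects the randomisation. For safety it mixes in two kinds of men who do not inform the question: those who took no double-blind drug, and those who took the other arm's capsule throughout. Under the conditions given below, both bring the arms closer together, and for safety that is the less cautious direction.

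The log-rank point is a separate inconsistency on an efficacy endpoint. A never-dosed man belongs to the analysis population but has no day zero. As written, he must either be dropped, in which case the analysis is not ITT, or be given a start date that the protocol does not define.

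**Working it through.** **Denominator.** Section 9.2.1 gives a difference of 1.8, SD 6, 90% power and 20% discontinuation; Section 9.1 gives two-sided alpha 0.05.

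- n per arm = 2 × (1.960 + 1.282)² × 6² / 1.8² = 233.5, rounded up to 234.
- 234 / 0.80 = 292.5, rounded up to 293 per arm, 586 in total.

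Both agree with the protocol. The sample size is not in dispute; 293 is used only as the safety denominator.

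**Illustrative rates.** Section 1.1 quotes ejaculation disorders in the earlier four-year study: 10.7% on combination and 3.7% on tamsulosin, a difference of 7.0 points. That study used tamsulosin 0.4 mg; this trial uses 0.2 mg for two years. The rates are a worked example, not a forecast.

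**Never-dosed men.** The protocol gives no rate, so the share f is an assumption. If f is equal in both arms and these men have no recorded events, each rate is multiplied by (1 − f), and so is the difference.

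| f (assumed) | Men per arm | Combination | Tamsulosin | Difference (points) |
|---|---|---|---|---|
| 0 | 0 | 10.70% | 3.70% | 7.00 |
| 1% | 2.9 | 10.59% | 3.66% | 6.93 |
| 2% | 5.9 | 10.49% | 3.63% | 6.86 |
| 3% | 8.8 | 10.38% | 3.59% | 6.79 |

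The risk ratio stays at 10.7 / 3.7 = 2.89 throughout.

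**Unequal shares.** The difference is 10.7(1 − f_c) − 3.7(1 − f_t).

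- Combination 3%, tamsulosin 0: 10.38 − 3.70 = 6.68 points.
- Combination 0, tamsulosin 3%: 10.70 − 3.59 = 7.11 points.

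The difference widens whenever f_t is more than 2.89 times f_c.

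**Wrong capsule throughout.** If an assumed share m of each arm receives the other arm's capsule for the whole period, the difference is multiplied by (1 − 2m): 6.86 points at 1% and 6.72 at 2%. With 2% of each problem, 7.0 × 0.98 × 0.96 = 6.59 points.

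**Power.** By a normal approximation (not Fisher's exact test), power at 293 per arm with no never-dosed men is 90.8%. With 2% never dosed it is 90.22% in all randomised men and 90.26% in dosed men only. Excluding never-dosed men therefore recovers almost no power; what changes is the reported percentage and difference.

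**Time origin.** Section 9.3.7.1 starts the clock at first dose, while 9.3.1 admits men with no first dose to the population in which the test is run. Both statements cannot be followed for a never-dosed man.

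**The case against.** The strongest objection is that this hardly matters here, and most of it stands. Appendix 2 places randomisation and dispensing of blinded drug at the same visit, after a four-week placebo run-in with a compliance check, so few men should go undosed. No never-dosed or misdispensing rate appears in the protocol; the shares above are assumptions.

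A reader might infer that the rule biases every safety comparison towards no difference. The documents do not support that, for four reasons.

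- Shrinkage needs similar never-dosed shares in the two arms; as shown, a sufficiently lopsided split widens the difference. If the true rates are equal, balanced dilution creates nothing.
- Never-dosed men need not be event-free. Section 7.4.7 collects adverse events from the start of run-in to the end of the two-year study period, and the adverse event tables in 9.3.7.2 are not limited to treatment-emergent events. The dilution of each arm's percentage is then smaller than tabulated. The difference still shrinks by (1 − f) if undosed men report events at the same rate in both arms.
- Much of the safety section is barely touched. Laboratory analyses require a post-baseline value, and PSA and residual volume are compared on change from baseline. The effect is mainly on adverse event and examination percentages.
- Both arms take open-label tamsulosin (Section 5.5), so a dispensing error misplaces only dutasteride exposure. Blinded drug is dispensed eight times (Visits 2 to 9), so one wrong bottle gives mixed exposure rather than a full swap.

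It can also be said that calling ITT the primary population leaves room for a supplementary as-treated analysis, and that Section 9.3.7.2 leaves full safety details to the RAP, which is not shown. That is fair, but the population for the main safety analysis is not one of the details deferred: the protocol states it twice. The AUR/surgery time origin adds no weight to the safety point and is kept separate.

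**Conclusion.** The point holds in a limited form. The protocol fixes a main safety population that fits its safety objective poorly, and it fixes a time origin that some members of the ITT population do not have. This is a stated rule rather than missing detail.

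The numerical consequence is probably very small. With an assumed 1-3% never dosed in each arm and few events among those men, a 7.0-point difference becomes about 6.9-6.8 points, using rates from a study of different tamsulosin dose and duration. Nothing in the protocol shows that never-dosed men or dispensing errors will be common, or that the Fisher comparisons are distorted to a degree that would change a conclusion. The reason to act is that the correction is conventional and nearly free, and is best made before unblinding.

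**What to change.** - **Section 9.3.1:** add a Safety population of randomised men who took at least one dose of double-blind medication, analysed by treatment actually received. State that men with mixed exposure are analysed as randomised unless they received the other treatment throughout.
- **Section 9.3.7.2:** replace ITT with this population for the safety analyses. Keep ITT, as randomised, for efficacy.
- **Section 9.3.7.1:** start time to AUR or BPH-related surgery at the randomisation date for the ITT log-rank test, and align the accompanying table by annual period, which now counts events from first dose. Because drug is dispensed at the randomisation visit, the start date should move little for dosed men.

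The cost is a short paragraph in each section and marginally smaller safety denominators. No new data are needed and the sample size does not change.

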## 9.3.2. Per Protocol Populations

The Per Protocol (PP) population will comprise all ITT subjects and who comply closely with the protocol. Major protocol deviations that would exclude subjects from the PP population will be defined and documented in the Reporting and Analysis Plan (RAP) prior to unblinding. The PP population will not be analysed if this population comprises more than 80% of the ITT population.

## 9.3.3. PPK Population

The PPK population wil comprise all ITT subjects of Chinese origin, recuited in China, randomized to receive the combination (0.5mg dutasteride and 0.2mg tamsulosin) who have available PPK samples.

## 9.3.4. Analysis Data Sets

Endpoints measured at specific visits and analysed in terms of visit numbers include: IPSS, Qmax, prostate volume, PSA, post void residual volume, suicidality and health outcomes. Analysis of the data collected in terms of visit numbers will be performed using two different approaches to account for missing data.

- 1. LOCF (Last Observation Carried Forward) analysis: This involves bringing (carrying) forward the last non-missing post-baseline assessment for subjects with missing visit data and/or for subjects who discontinued from the study.
- 2. At Visit analysis: Missing values at post-baseline assessments are not replaced and are regarded as missing.

The LOCF approach will be considered primary. If the LOCF and At Visit results are not consistent with regard to the statistical analyses and conclusions, then further data analyses will be undertaken.

Endpoints measured in terms of event calendar days and analyzed in terms of survival methodology include AUR and BPH-related surgical intervention. These analyses will use the observed-cases approach in which actual date of event is used; missing values post-baseline are not replaced and are regarded as missing.

Analysis datasets will be created with a structure to reflect the above noted approaches for each endpoint.

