## 7.2.2.5. End of Study Treatment Assessments

During the study period that is between the scheduled visits, if a subject discontinues study treatment permanently after Visit 2 (post-randomisation) for any reason, other than lost to follow-up, the investigator should make every effort to schedule a visit by the subject to the study site and complete the following assessment:

- Concomitant medications
- Adverse events
- Physical exam including vital signs, DRE and qualitative breast examination
- Obtain blood samples for hematology, clinical chemistry and PSA determinations
- Administer health outcome questionnaires (IPSS, BHS,BII and PAS-SFI)
- Administration of C-SSRS questionnaire
- Record any episodes of AUR, and, BPH-related prostatic surgery or minimally-invasive/non-surgical interventions
- Record any episodes of UTI/urosepsis, urinary incontinence (first episode or consistent worsening), and renal insufficiency
- Retrieve any unused double-blind study medication, assess compliance and record date of last dose of study medication
- Discuss the biannual follow-up phone call schedule
- Complete subject eCRF

If the decision for a subject's study treatment discontinuation is made during a regularly scheduled visit, the procedure that are stated above should be completed, in addition to any scheduled procedure that is not listed above.

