## 7.3.9. Suicidality

Dutasteride is considered to be an active compound in human central nervous system (CNS) that may affect mood or behavior via effects on the CNS (directly or indirectly). A GSK review of published literature and clinical trial data for dutasteride has shown that dutasteride is not associated with an increased risk of suicidal thinking or behavior when given to this patient population.

There has been some concern that some CNS-active drugs may be associated with an increased risk of suicidal thinking or behavior when given to some subjects with certain conditions. Although these drugs and other similar drugs of the same class have not been associated with an increased risk of suicidal thinking or behavior when given to this patient population, GSK considers it important to monitor for such events before or during clinical studies with compounds such as this.

Subjects in Study ARI114265 will be assessed for suicidality and unusual changes in behavior using the Columbia Suicide Severity Rating Scale (C-SSRS). To protect subjects in the study, scores from C-SSRS tests will be reviewed in real time by the investigator and appropriate advice given to participants. Consideration should be given to discontinuing study treatments in subjects who experience signs of suicidal ideation or behavior. Refer to Section 7.4.6 for more information.

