## 7.4.6. Suicidality Monitoring

Assessment of suicidality will be performed using the C-SSRS which will be administered at baseline, during the course of study, and at the end of the study. Training to investigators and sites on suicidality assessment will be integral to the study implementation. Any AEs which, in the investigator's opinion, are possibly suicidality-related, will be recorded in the Possible Suicidality Related Adverse Event form (PSRAE); a supplemental CRF form designed to collect detailed information on the circumstances of reported AEs related to suicidality.

The 'baseline/screening' version of C-SSRS will be used at the pre-screening visit (V1a). The 'since last visit' version of C-SSRS will be used at Visits 4, 6 and 10 (6, 12 and 24 months post randomization respectively).

A trained rater will administer the C-SSRS questionnaires according to the schedule detailed in Table 1. The C-SSRS questionnaire will be completed during the clinical visit separately from the medical history and the standard adverse event questions.

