To describe the laboratory values at baseline, the frequency of subjects with a threshold laboratory value at baseline among subjects with a baseline laboratory value and a post baseline laboratory value will be computed by treatment group. Among subjects whose baseline value was not classified as threshold, the frequency of subjects with threshold values at any post baseline laboratory will be computed by treatment group. Among subjects whose baseline value was not high threshold, the frequency of subjects with high threshold values at any post baseline laboratory will be computed by treatment group. Among subjects whose baseline value was not low threshold, the frequency of subjects with low threshold values at any post baseline laboratory will be computed by treatment group.

Differences in laboratory values between baseline and the final scheduled laboratory assessment will be calculated for each laboratory test and summarized by treatment group.

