## Suicidality

To protect subjects in the study, scores from C-SSRS tests will be reviewed in real time by the investigator and appropriate advice given to participants.

The C-SSRS scale has 10 outcomes, with binary (yes/no) responses. At the end of study, results will be assessed as follows:

- Suicidal ideation will be defined as a positive response at any time during treatment to any one of the five suicidal ideation questions (Categories 1-5) on the C-SSRS.
- Suicidal behavior will be defined as a positive response at any time during treatment to any one of the five suicidal behaviour questions (Categories 6-10) on the C-SSRS.
- Suicidal ideation or behavior will be defined as a positive response at any time during treatment to any one of the ten suicidal ideation and behaviour questions (Categories 1-10) on the C-SSRS.

The numbers of subjects with a positive response for suicidal ideation or suicidal behaviour will be reported at baseline and during study treatment at Visits 4, 6 and 10 (6, 12 and 24 months post randomization respectively). Scores on treatment will be compared with baseline scores and, for Visits 6 and 10, with scores at last visit to determine the incidence of treatment-emergent suicidality. An increase in C-SSRS total score to 4 or 5 will be considered as serious treatment-emergent suicidality. Due to the low numbers of subjects expected to exhibit suicidal behaviours, formal statistical testing will not be performed.

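### Suicidality is on the list of endpoints analysed with LOCF as primary, although the on-treatment C-SSRS asks only about the time since the last visit; the plan also leaves open where the end-of-treatment C-SSRS is counted

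*Protocol*

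**What the plan says.** Section 9.3.4 names the endpoints analysed by visit number, including "prostate volume, PSA, post void residual volume, suicidality and health outcomes". It gives two approaches for them, LOCF and At Visit, and states: "The LOCF approach will be considered primary". LOCF there means bringing "forward the last non-missing post-baseline assessment for subjects with missing visit data and/or for subjects who discontinued from the study". Under At Visit, missing values stay missing. Appendix 8 records that suicidality was added to this list with Amendment 2; the current text keeps it.

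Section 7.4.6 uses the baseline/screening C-SSRS at Visit 1a. After randomisation the since-last-visit "version of C-SSRS will be used at Visits 4, 6 and 10". When treatment is stopped early, section 7.2.2.5 also requires "Administration of C-SSRS questionnaire", and Appendix 2 repeats this. Section 6.3 plans no further clinic assessments after that visit, only six-monthly telephone contact for other clinical events.

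Section 9.3.7.2.1 (Suicidality) defines three per-subject outcomes (ideation, behaviour, or either), each a positive answer at any point during treatment. Separately, the numbers of positive subjects "will be reported at baseline and during study treatment at Visits 4, 6 and 10". Treatment-emergent suicidality is found by comparing on-treatment scores with baseline and, for Visits 6 and 10, with the scores at the last visit. No formal test is planned.

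**The concern.** LOCF assumes that the last recorded value is a tolerable stand-in for the missing one. That can at least be argued for a state such as prostate volume. A since-last-visit answer is different: it reports whether something happened in a closed interval and says nothing about later intervals. Carrying it forward creates by-visit safety results for time that nobody asked about.

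Early stoppers are the men most affected, and they matter most here, because section 7.3.9 links the scale to stopping: "Consideration should be given to discontinuing study treatments in subjects who experience signs of suicidal ideation or behavior". For such a man the last C-SSRS is normally the one taken at the End of Study Treatment visit. The by-visit display names no row for that visit, and the protocol does not say whether it falls within the treatment period for the per-subject outcomes. The number of men shown as positive therefore depends on rules that are ill-suited to the instrument or not written down.

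**Working it through.** **1. Which approach applies to C-SSRS.** Section 9.3.7 says the approach is assigned in later sections. The texts on PSA, post-void residual volume, BHS, BII and PAS-SFI each name LOCF and At Visit. The suicidality text names neither. The only assignment in the protocol is therefore the list in 9.3.4, with LOCF primary.

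**2. One man positive only at his End of Study Treatment C-SSRS.** Visits 4, 6 and 10 fall at Months 6, 12 and 24. The result is carried to every later scheduled visit.

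| Treatment stops at | LOCF shows him positive at | At Visit | Per-subject outcome, if the stop visit counts |
|---|---|---|---|
| Month 4 | Visits 4, 6, 10 | none | 1 |
| Month 9 | Visits 6, 10 | none | 1 |
| Month 18 | Visit 10 | none | 1 |

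The At Visit column assumes that the stop visit is not assigned to a scheduled visit.

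**3. Denominators from the plan.** The protocol gives no figure for suicidality, so the arm sizes come from 9.2.1 (difference 1.8, SD 6, two-sided alpha 0.05, 90% power, 20% discontinuation):

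- n per arm = 2 × (1.960 + 1.2816)² × 6² / 1.8² = 233.5, rounded up to 234, as stated.
- Randomised per arm = 234 / (1 − 0.20) = 292.5, rounded up to 293, as stated.

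**4. Positives among early stoppers.** Let k men per arm be positive only at the stop visit and all other men negative (assumption, k = 1 to 5). At Month 24:

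- LOCF: k/293, i.e. 1/293 = 0.34% to 5/293 = 1.71%.
- At Visit: 0/234.
- Per-subject outcome: k/293 if the stop visit counts as treatment period, 0/293 if it does not.

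**5. Negatives among early stoppers.** Let one man per arm who stays on treatment be positive at Month 24 and all early stoppers be negative. Observed: 1/234 = 0.43%. LOCF: 1/293 = 0.34%. The rate falls by the factor 234/293 = 0.80 only because men not seen at Month 24 enter the denominator as negative.

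In steps 4 and 5, 293 is the largest possible LOCF denominator, since a man with no post-baseline C-SSRS has nothing to carry; 234 assumes that every man still on treatment is assessed.

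**6. The emergent comparison.** A man stops at Month 9. His stop-visit result is carried to Visits 6 and 10. At Visit 6 it can still exceed his observed Visit 4 score. At Visit 10 it is compared with a copy of itself, so no increase is possible. The same holds at both Visits 6 and 10 for a man whose last C-SSRS was at Visit 4 or before. Such men enter as assessed without emergent suicidality.

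**The case against.** The strongest reply is that LOCF for C-SSRS rests on one word in a list. Section 9.3.7 speaks of using the approaches as appropriate, the suicidality text never invokes LOCF, and 9.3.7.2 leaves full safety detail to the reporting and analysis plan, which is not at hand. This lowers the chance that the tables would be built that way. It does not remove the point, because the only rule the protocol states for this endpoint is the wrong one.

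A reader might infer that a man who stops because of suicidality must be either missed or counted at visits he never attended. The protocol does not support that. The per-subject outcomes in 9.3.7.2.1 are not tied to a visit and can count him once. Table 1, footnote i, also uses the Visit 10 column for the early stop, so his result might be placed at Visit 10. What remains open is whether the stop visit counts as treatment period, which C-SSRS version is used there (7.4.6 names none), and how it is placed for analysis.

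A reader might also suppose that a Month 6 negative would routinely be carried to Month 24. Where the stop-visit C-SSRS is done, that is the value carried; the Month 6 case arises mainly for men lost to follow-up or not attending.

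Suicidality can also surface through other routes: the supplemental adverse event form, AE and SAE collection, real-time review by the investigator, and the comparison of AEs leading to withdrawal. These protect the individual and the overall safety record, but they do not correct the C-SSRS tables.

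Finally, a reader might extend the point to laboratory data, because "Differences in laboratory values between baseline and the final scheduled laboratory assessment will be calculated". That does not carry over well: abnormal and threshold counts use any post-baseline value, so early-stop samples enter them, and only the change summary has the restrictive wording.

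**Conclusion.** The point holds, with limited reach. Followed as written, section 9.3.4 produces by-visit suicidality results at Visits 6 and 10, and at Visit 4 after a very early stop, for periods that were wholly or partly unassessed. The per-subject outcomes could give the right count, but the protocol does not say that the End of Study Treatment C-SSRS enters them.

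The size depends on k, which is unknown, and on the 20% discontinuation assumed for planning. One positive early stopper appears at one to three visits under LOCF, depending on when he stops. LOCF does not always lower the rate: for stop-visit positives it gives the same Month 24 fraction as a per-subject count that includes them, and it lowers the rate where early stoppers are negative. Taking 20% of all randomised men as the number with an invented Month 24 result would be an upper bound, not an estimate, because some of them will have no post-baseline C-SSRS to carry.

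No power or sample size figure changes. The consequence is confined to descriptive safety tables, which are the only planned analysis of a scale that was added to the protocol for safety monitoring.

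**What to change.** - **Section 9.3.4:** delete suicidality from the list of endpoints analysed by LOCF and At Visit. State that C-SSRS is summarised as observed, without replacement of missing assessments.
- **Section 9.3.7.2.1, by-visit display:** give the number assessed at each visit as the denominator, and add the End of Study Treatment visit as its own row.
- **Section 9.3.7.2.1, per-subject outcomes:** state that a positive post-baseline C-SSRS up to and including the End of Study Treatment visit counts, once per man.
- **Section 9.3.7.2.1, emergent suicidality:** base the comparison with the last visit on observed assessments only.
- **Section 7.4.6:** name the C-SSRS version used at the End of Study Treatment visit.

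The cost is wording in the protocol and the reporting and analysis plan; the protocol already calls for these data. The added row will mix different lengths of treatment, which a footnote can say.
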